#### Group B Response for hematopoietic system^2

Response	Platelet count	Hemoglobin	Neutrophils
CR	>100 x 10  /L	>11 g/dL	>1.5 x 10  /L
CRi	If meets criteria from Group A but does not meet criteria from Group B		
PR	>100 x 10  /L or increase ≥50% over baseline	>11 g/dL or increase ≥50% over baseline	>1.5 x 10  /L or >50% improvement over baseline
SD	Failure to attain CR/CRi/PR or PD		
Relapsed disease or PD	Appearance of any new lesions; at least one of the above criteria. Isolated progressive lymphocytosis in the setting of reduced lymph node size or organomegaly or improvement in hemoglobin/platelets will not be considered progressive disease		

 Hallek M, et al. Guidelines for the diagnosis and treatment of chronic lymphocytic leukemia updating the National Cancer Institute-Working Group 1996 Guidelines. Blood 2008; 111:5446-5456

 All values are without transfusion or hematopoietic growth factors

**Appendix K: Eastern Cooperative Oncology Group (ECOG) Performance status**

Score	Performance Status
0	Fully active, able to carry on all pre-disease performance without restriction.
1	Restricted in physically strenuous activity but ambulatory and able to carry out work of a light or sedentary nature, e.g. light housework, office work.
2	Ambulatory and capable of all self-care but unable to carry out any work activities. Up and about more than 50% of waking hours.
3	Capable of only limited self-care, confined to bed or chair more than 50% of waking hours.
4	Completely disabled. Cannot carry on any self-care. Totally confined to bed or chair.
5	Dead

## Appendix L: International Myeloma Working Group (IMWG) uniform response criteria for multiple myeloma

Response	IMWG Criteria
sCR	CR as defined below plus normal FLC ratio and absence of clonal cells in bone marrow  by immunohistochemistry or immunofluorescence 
CR	Negative immunofixation on the serum and urine and disappearance of any soft tissue plasmacytomas and < 5% plasma cells in bone marrow 
VGPR	Serum and urine M-component detectable by immunofixation but not on electrophoresis or ≥ 90% reduction in serum M-component plus urine M-component < 100 mg per 24 hr
PR	> 50% reduction of serum M-protein and reduction in 24 hours urinary M-protein by >90% or to < 200 mg/24 h  If the serum and urine M-protein are unmeasurable,  a > 50% decrease in the difference between involved and uninvolved FLC levels is required in place of the M-protein criteria  If serum and urine M-protein are not measurable, and serum free light assay is also not measurable, > 50% reduction in plasma cells is required in place of M-protein, provided baseline bone marrow plasma cell percentage was > 30%  In addition to the above listed criteria, if present at baseline, a > 50% reduction in the size of soft tissue plasmacytomas is also required
SD	Not meeting criteria for CR, VGPR, PR, or progressive disease
PD 	Increase of > 25% from lowest response value in any one or more of the following:  Serum M-component and/or (the absolute increase must be > 0.5 g/dL)   Urine M-component and/or (the absolute increase must be > 200 mg/24 h)  Only in patients without measurable serum and urine M-protein levels; the difference between involved and uninvolved FLC levels. The absolute increase must be > 10 mg/dL  Bone marrow plasma cell percentage; the absolute percentage must be > 10%   Definite development of new bone lesions or soft tissue plasmacytomas or definite increase in the size of existing bone lesions or soft tissue plasmacytomas  Development of hypercalcaemia (corrected serum calcium > 11.5 mg/dL or 2.65 mmol/L) that can be attributed solely to the plasma cell proliferative disorder
Relapse	Clinical relapse requires one or more of:  Direct indicators of increasing disease and/or end organ dysfunction (CRAB features).  It is not used in calculation of time to progression or progression-free survival but is listed here as something that can be reported optionally or for use in clinical practice  Development of new soft tissue plasmacytomas or bone lesions  Definite increase in the size of existing plasmacytomas or bone lesions. A definite increase is defined as a 50% (and at least 1 cm) increase as measured serially by the sum of the products of the cross-diameters of the measurable lesion  Hypercalcemia (> 11.5 mg/dL) [2.65 mmol/L]  Decrease in haemoglobin of > 2 g/dL [1.25 mmol/L]  Rise in serum creatinine by 2 mg/dL or more [177 mmol/L or more]

---

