**Table 6-3 Ribociclib related toxicity management guidelines**

Toxicity	Grade	Dose Adjustment and Management Recommendations
Thrombocytopenia	Grade 1 ≥75 x 10  /L	No dose adjustment required.
	Grade 2 ≥50 x 10  /L – <75 x 10  /L	Dose interruption until recovery to grade ≤1. Re-initiate ribociclib at the same dose.
	Grade 3 ≥25 x 10  /L - <50 x 10  /L	Dose interruption until recovery to grade ≤1. Re-initiate ribociclib at the same dose level. If toxicity recurs at grade 3: temporary dose interruption until recovery to grade ≤1 and reduce ribociclib to the next lower dose level.
	Grade 4 <25 x 10  /L	Dose interruption until recovery to grade ≤1. Re-initiate ribociclib at the next lower dose level. If toxicity recurs at grade 4: discontinue ribociclib.
Absolute neutrophil count (ANC)	Grade 1 ≥1.5 x 10  /L	No dose adjustment required.
	Grade 2 ≥1.0 - <1.5 x 10  /L	No dose adjustment required.

Toxicity	Grade	Dose Adjustment and Management Recommendations
	Grade 3 $\geq 0.5 - <1.0 \times 10^9/L$	Dose interruption until recovery to $\geq 1.0 \times 10^9/L$ . Re-initiate ribociclib at the same dose level. If toxicity recurs at grade 3: temporary dose interruption until recovery to $\geq 1.0 \times 10^9/L$ . If resolved within $\leq 7$ days, then maintain dose level. If resolved $>7$ days, then reduce ribociclib dose to the next lower dose level.
	Grade 4 $<0.5 \times 10^9/L$	Dose interruption until recovery to $\geq 1.0 \times 10^9/L$ . Re-initiate LEE011 at the next lower dose level. If toxicity recurs at grade 4: temporary dose interruption until recovery to $\geq 1.0 \times 10^9/L$ and reduce LEE011 at the next lower dose level.
Febrile neutropenia	Grade 3 ANC $<1.0 \times 10^9/L$ with [a single temperature of $>38.3$ degrees C (101 degrees F) or a sustained temperature of $\geq 38$ degrees C (100.4 degrees F) for more than one hour]	Dose interruption until improvement of ANC $\geq 1.0 \times 10^9/L$ and no fever. Restart at the next lower dose level. If febrile neutropenia recurs, discontinue ribociclib.
	Grade 4 Life-threatening consequences; urgent intervention indicated	Discontinue ribociclib.
Anemia (Hemoglobin)	Grade 1 $\geq 10.0 - LLN$ g/dL	No dose adjustment required.
	Grade 2 $\geq 8.0 - <10.0$ g/dL	No dose adjustment required.
	Grade 3 $<8.0$ g/dL	Dose interruption until recovery to grade $\leq 2$ . Re-initiate ribociclib at the same dose.

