#### 10.5.3.1.2 Laboratory abnormalities

All laboratory values will be converted into SI units and the severity grade will be calculated using appropriate common terminology criteria (CTCAE v4.03).

A severity grade of 0 will be assigned when the value is within normal limits. For lab parameters for which severity grades are determined both through normal limits and absolute cut-offs, in the unlikely case when a local laboratory normal range overlaps into the higher (i.e. non-zero) CTCAE grade, the laboratory value will still be taken as within normal limits and assigned a CTCAE grade of zero.

A listing of laboratory values will be provided by laboratory parameter, patient, and treatment arm. A separate listing will display notable laboratory abnormalities (i.e., newly occurring CTCAE grade 3 or 4 laboratory toxicities). Lab values collected later than 30 days after study treatment discontinuation will be flagged in the listings

The following by-group summaries will be generated separately for hematology, and biochemistry parameters:

[figure not shown]
- shift tables using CTCAE grades to compare baseline to the worst on-treatment value
- for laboratory tests where CTCAE grades are not defined, shift tables using the low/normal/high/(low and high) classification to compare baseline to the worst on-treatment value.
- listing of all laboratory data with values flagged to show the corresponding CTCAE grades and the classifications relative to the laboratory normal ranges.

[figure not shown]

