CR	Bone marrow: Age-adjusted normocellularity; <5% blasts; ≤grade 1 MF † and Peripheral blood: Hemoglobin ≥100 g/L and <UNL; neutrophil count ≥ 1 X 10  /L and <UNL; Platelet count ≥100 X 10  /L and <UNL; <2% immature myeloid cells ‡ and Clinical: Resolution of disease symptoms; spleen and liver not palpable; no evidence of EMH
PR	Peripheral blood: Hemoglobin ≥100 g/L and <UNL; neutrophil count ≥1 X 10  /L and <UNL; platelet count ≥100 X 10  /L and <UNL; <2% immature myeloid cells ‡ and Clinical: Resolution of disease symptoms; spleen and liver not palpable; no evidence of EMH or Bone marrow: Age-adjusted normocellularity; <5% blasts; ≤grade 1 MF † , and peripheral blood: Hemoglobin ≥85 but <100 g/L and <UNL; neutrophil count ≥1 X 10  /L and <UNL; platelet count ≥50, but <100 X 10  /L and <UNL; <2% immature myeloid cells ‡ and Clinical: Resolution of disease symptoms; spleen and liver not palpable; no evidence of EMH
Clinical improvement (CI)	The achievement of anemia, spleen or symptoms response without progressive disease or increase in severity of anemia, thrombocytopenia, or neutropenia §
Anemia response	Transfusion-independent patients: a ≥20 g/L increase in hemoglobin level  Transfusion-dependent patients: becoming transfusion-independent ^
Spleen response#	A baseline splenomegaly that is palpable at 5-10 cm, below the LCM, becomes not palpable ** or A baseline splenomegaly that is palpable at >10 cm, below the LCM, decreases by ≥50% ** A baseline splenomegaly that is palpable at <5 cm, below the LCM, is not eligible for spleen response A spleen response requires confirmation by MRI or computed tomography showing ≥35% spleen volume reduction
Symptoms response	A ≥50% reduction in the MPN-SAF TSS ††
Progressive disease	Appearance of a new splenomegaly that is palpable at least 5 cm below the LCM or A ≥100% increase in palpable distance, below LCM, for baseline splenomegaly of 5-10 cm or A 50% increase in palpable distance, below LCM, for baseline splenomegaly of >10 cm or Leukemic transformation confirmed by a bone marrow blast count of ≥20% or A peripheral blood blast content of ≥20% associated with an absolute blast count of ≥1 X 10(9)/L that lasts for at least 2 weeks
Stable disease	Belonging to none of the above listed response categories

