§See above for definitions of anemia response, spleen response, and progressive disease. Increase in severity of anemia constitutes the occurrence of new transfusion dependency or a  $\geq 20\%$  decrease in hemoglobin level from pretreatment baseline that lasts for at least 12 weeks. Increase in severity of thrombocytopenia or neutropenia is defined as a 2-grade decline, from pretreatment baseline, in platelet count or absolute neutrophil count, according to the Common Terminology Criteria for Adverse Events (CTCAE) version 4.0. In addition, assignment to CI requires a minimum platelet count of  $\geq 25\,000 \times 10^9/L$  and absolute neutrophil count of  $\geq 0.5 \times 10^9/L$ .

||Applicable only to patients with baseline hemoglobin of  $<100\text{ g/L}$ . In patients not meeting the strict criteria for transfusion dependency at the time of study enrollment (see as follows), but have received transfusions within the previous month, the pre-transfusion hemoglobin level should be used as the baseline.

^Transfusion dependency before study enrollment is defined as transfusions of at least 6 units of packed red blood cells (PRBC), in the 12 weeks prior to study enrollment, for a hemoglobin level of  $<85\text{ g/L}$ , in the absence of bleeding or treatment-induced anemia. In addition, the most recent transfusion episode must have occurred in the 28 days prior to study enrollment. Response in transfusion-dependent patients requires absence of any PRBC transfusions during any consecutive “rolling” 12-week interval during the treatment phase, capped by a hemoglobin level of  $\geq 85\text{ g/L}$ .

Response category	Definition
	#In splenectomized patients, palpable hepatomegaly is substituted with the same measurement strategy. **Spleen or liver responses must be confirmed by imaging studies where a $\geq 35\%$ reduction in spleen volume, as assessed by MRI or CT, is required. Furthermore, a $\geq 35\%$ volume reduction in the spleen or liver, by MRI or CT, constitutes a response regardless of what is reported with physical examination.

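### Appendices L and M carry unit errors in decision limits: the myeloma calcium criterion states two unequal thresholds as one, and the myelofibrosis improvement criterion sets a platelet floor that cannot be met as printed

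*Protocol*

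**What the plan says.** **Myeloma (Protocol Appendix L).** Among the alternative progression criteria is "Development of hypercalcaemia (corrected serum calcium > 11.5 mg/dL or 2.65 mmol/L", provided it can be attributed solely to the plasma cell disorder. The clinical relapse row repeats the pair, "Hypercalcemia (> 11.5 mg/dL) [2.65 mmol/L". It also lists "Decrease in haemoglobin of > 2 g/dL [1.25 mmol/L" and "Rise in serum creatinine by 2 mg/dL or more [177 mmol/L or more". That row, and a footnote to the table, say that clinical relapse does not enter the calculation of progression-free survival.

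**Myelofibrosis (Protocol Appendix M).** A footnote to the clinical improvement (CI) category says that "assignment to CI requires a minimum platelet count of" at least 25 000 × 10⁹/L, together with neutrophils of at least 0.5 × 10⁹/L. For complete response the table asks for "Platelet count ≥100 X 10 9 /L and <UNL", and one route to partial response uses platelets from 50 to below 100 × 10⁹/L. Relapse includes ceasing to qualify for CI or better after an earlier CR, PR or CI.

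**Use of these tables.** Symptomatic myeloma is eligible (Protocol Section 5.2, criterion 9c) and is assessed by Appendix L (Section 7.2.1.3). Myelofibrosis is assessed by Appendix M (Section 7.2.1.4). Progression or relapse is a PFS event (Protocol Section 10.5.2; SAP Section 4.4). Progression before 16 weeks means that clinical benefit was not achieved (SAP Section 4.1).

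**The concern.** These appendices are the only operative definition of response and progression for the two diseases. Where one criterion carries two limits that are not equivalent, two investigators can follow the protocol and classify the same patient differently. The myeloma calcium pair sits in the progression row, the one that feeds PFS and the 16-week status. Calcium and albumin belong to the scheduled biochemistry panel (Protocol Section 7.2.2.5.2), so the criterion can be evaluated throughout treatment.

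In myelofibrosis the difficulty is a floor that nobody can reach. If CI can never be assigned, the step between partial response and relapse disappears, and relapse is a PFS event.

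**Working it through.** **Inputs from the documents:** calcium 11.5 mg/dL and 2.65 mmol/L, haemoglobin 2 g/dL and 1.25 mmol/L, and creatinine 2 mg/dL and 177 mmol/L (all Appendix L); CI platelet minimum 25 000 × 10⁹/L and CR platelet floor 100 × 10⁹/L (Appendix M); grade 4 thrombocytopenia, "Grade 4 <25 x 10 9 /L" (Table 6-3); the highest platelet limit in any response appendix, 450 × 10⁹/L (Appendix I).

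**Assumed constants, not in the documents:** molar mass of calcium 40.08 g/mol (range tried 40.0 to 40.1), creatinine 113.12 g/mol, haemoglobin monomer about 16 125 g/mol.

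**Formula:** mmol/L = (mg/dL × 10) / molar mass.

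1. *Do the table's pairs aim to be equivalents?* Haemoglobin: 2 g/dL = 20 g/L, and 20 / 16 125 × 1000 = 1.24 mmol/L. The stated figure is 1.25, so this pair reproduces.
2. *Calcium, mg/dL to mmol/L:* 11.5 × 10 / 40.08 = 2.87 mmol/L (2.868 to 2.875 over the range). The stated 2.65 does not reproduce.
3. *Calcium, mmol/L to mg/dL:* 2.65 × 40.08 / 10 = 10.62 mg/dL (10.60 to 10.63).
4. *Gap:* 2.869 − 2.65 = 0.22 mmol/L, which is 0.219 / 2.65 = 8%; in the other unit, 11.5 − 10.62 = 0.88 mg/dL. Rounding cannot explain it: equality would need a molar mass of 115 / 2.65 = 43.4.
5. *Consequence:* corrected calcium above 10.62 and up to 11.5 mg/dL exceeds the SI figure but not the conventional one.
6. *Platelets:* 25 000 / 100 = 250 times the CR floor; 25 000 / 25 = 1000 times the grade 4 limit; 25 000 / 450 = 56 times the highest platelet limit in the response appendices. CR also requires a count below the upper normal limit, so a patient with CR-level platelets fails the CI minimum. For reference, 25 000 per microlitre equals 25 × 10⁹/L. The neutrophil floor in the same sentence, 0.5 × 10⁹/L, is on the ordinary scale.
7. *Creatinine:* 2 × 10 / 113.12 = 0.177 mmol/L = 177 µmol/L. The printed 177 mmol/L is about 1000 times too large.

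**The case against.** Several points against the concern have force.

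- **SI conversion.** A reader might infer that progression will be judged on the lower limit, because the protocol says "All laboratory values will be converted into SI units". That sentence is in Section 10.5.3.1.2, under the safety objectives, and governs grading, listings and shift tables. Response is judged by the local investigator (Section 7.2.1) from local laboratory values. Nothing says that progression is derived from the converted safety data. The inference fails, but the two limits are unequal without it.
- **Everyone in the calcium band.** It is tempting to say that every myeloma patient between 10.62 and 11.5 mg/dL is classified in opposite ways. The hypercalcaemia must develop and be attributable solely to the disease, and a patient who has already progressed by M-component, light chains, marrow, bone lesions or plasmacytoma is classified the same either way. Only patients for whom calcium is the sole criterion are affected.
- **Myelofibrosis and the main endpoints.** One might infer that an unreachable CI lowers the clinical benefit rate or response rate. SAP Section 4.1 counts CR, PR or stable disease of at least 16 weeks and does not mention CI. Appendix M makes stable disease the residual category, so a patient denied CI can still count as a benefit. Overall response needs PR or better. What stands is the relapse route.
- **Obvious misprint.** The platelet figure is in a footnote, and a sensible assessor would see that it cannot be meant. That is likely, but the text then leaves each assessor to choose a replacement.
- **Creatinine.** The row is excluded from PFS and the mg/dL figure is usable. This item is only a correction of the text.
- **Reach.** Neither disease is among the tumors expected in Section 5.1 or the eight example Bayesian cohorts. Hematologic types with fewer than 4 patients are only listed for benefit and response (SAP Sections 4.1 and 4.2), and Amendment 3 records that enrollment closed in May 2015. This limits severity; it does not make the figures consistent.

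**Conclusion.** The point holds, with minor severity. The calcium pair is two limits 0.22 mmol/L (8%) apart in a row that determines PFS and can determine 16-week benefit. It affects only patients whose sole progression criterion is disease-attributed corrected calcium between 10.62 and 11.5 mg/dL. The CI platelet minimum is 250 times the CR floor in its own table. Applied literally, it turns loss of partial response into a relapse, and so a PFS event, for a patient who is still improved. No effect of the platelet figure on clinical benefit rate or overall response rate is shown. The creatinine unit is wrong by a factor of about 1000, with no effect on PFS.

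The conversions rest only on standard molar masses, and the calcium result does not change over the range tried. The number of patients affected cannot be estimated, because the documents give no myeloma or myelofibrosis counts. PFS is summarized by tumor type only for types with ten or more patients (SAP Section 4.4), so an isolated misclassification would mostly appear in the combined curve.

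The documents do not show which calcium figure was intended. Nor do they state 25 × 10⁹/L as the CI limit: that figure appears only as the grade 4 thrombocytopenia cut-off in Table 6-3, which serves another purpose.

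**What to change.** 1. **Appendix L, calcium:** reconcile the two figures against the source criteria into one limit with its true equivalent in the other unit, in both the progression and the relapse row. The consistent pairs are 11.5 mg/dL with 2.87 mmol/L, or 10.62 mg/dL with 2.65 mmol/L; the choice is the sponsor's.
2. **Appendix M, CI footnote:** reconcile the platelet figure and its unit with the source criteria and with the table's other platelet limits.
3. **Appendix L, creatinine:** correct the bracket to 177 µmol/L.
4. **Data already collected:** check any myeloma or myelofibrosis classification that relied on these figures, and record the limit actually applied in the study report.

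The cost is three corrected criteria in the appendices, with the calcium pair changed in two places, and a short check of what may be few records or none. No sample size, error rate or model input changes.

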**Response      IMWG Criteria**

---

1. BGM Durie et al. International uniform response criteria for multiple myeloma. Leukemia (2006) 1-7.

Adapted from Durie BGM, et al. Leukemia 2006; 20: 1467-1473; and Kyle RA, Rajkumar SV. Leukemia 2008;23:3-9

Note: A clarification to IMWG criteria for coding CR and VGPR in patients in whom the only measurable disease is by serum FLC levels: CR in such patients is defined as a normal FLC ratio of 0.26–1.65 in addition to CR criteria listed above. VGPR in such patients is defined as a >90% decrease in the difference between involved and unininvolved free light chain (FLC) levels.

2. Confirmation with repeat bone marrow biopsy not needed.
3. Presence/absence of clonal cells is based upon the kappa/lambda ratio. An abnormal kappa/lambda ratio by immunohistochemistry and/or immunofluorescence requires a minimum of 100 plasma cells for analysis. An abnormal ratio reflecting presence of an abnormal clone is kappa/lambda of > 4:1 or < 1:2.
4. All relapse categories require two consecutive assessments made at any time before classification as relapse or disease progression and/or the institution of any new therapy. In the IMWG criteria, CR patients must also meet the criteria for progressive disease shown here to be classified as progressive disease for the purposes of calculating time to progression and progression-free survival. The definitions of relapse, clinical relapse and relapse from CR are not to be used in calculation of time to progression or progression-free survival.
5. For progressive disease, serum M-component increases of >1 gm/dL are sufficient to define relapse if starting M-component is >5 g/dL.
6. Relapse from CR has the 5% cut-off versus 10% for other categories of relapse.

For purposes of calculating time to progression and progression-free survival, CR patients should also be evaluated using criteria listed above for progressive disease.

---

**Appendix M: Criteria for Response assessment in Myelofibrosis (based on modified IWG-MRT guidelines and European LeukemiaNet (ELN) consensus report)**

Response category	Definition
CR	Bone marrow: Age-adjusted normocellularity; <5% blasts; ≤grade 1 MF † and Peripheral blood: Hemoglobin ≥100 g/L and <UNL; neutrophil count ≥ 1 X 10  /L and <UNL; Platelet count ≥100 X 10  /L and <UNL; <2% immature myeloid cells ‡ and Clinical: Resolution of disease symptoms; spleen and liver not palpable; no evidence of EMH
PR	Peripheral blood: Hemoglobin ≥100 g/L and <UNL; neutrophil count ≥1 X 10  /L and <UNL; platelet count ≥100 X 10  /L and <UNL; <2% immature myeloid cells ‡ and Clinical: Resolution of disease symptoms; spleen and liver not palpable; no evidence of EMH or Bone marrow: Age-adjusted normocellularity; <5% blasts; ≤grade 1 MF † , and peripheral blood: Hemoglobin ≥85 but <100 g/L and <UNL; neutrophil count ≥1 X 10  /L and <UNL; platelet count ≥50, but <100 X 10  /L and <UNL; <2% immature myeloid cells ‡ and Clinical: Resolution of disease symptoms; spleen and liver not palpable; no evidence of EMH
Clinical improvement (CI)	The achievement of anemia, spleen or symptoms response without progressive disease or increase in severity of anemia, thrombocytopenia, or neutropenia §
Anemia response	Transfusion-independent patients: a ≥20 g/L increase in hemoglobin level  Transfusion-dependent patients: becoming transfusion-independent ^
Spleen response#	A baseline splenomegaly that is palpable at 5-10 cm, below the LCM, becomes not palpable ** or A baseline splenomegaly that is palpable at >10 cm, below the LCM, decreases by ≥50% ** A baseline splenomegaly that is palpable at <5 cm, below the LCM, is not eligible for spleen response A spleen response requires confirmation by MRI or computed tomography showing ≥35% spleen volume reduction
Symptoms response	A ≥50% reduction in the MPN-SAF TSS ††
Progressive disease	Appearance of a new splenomegaly that is palpable at least 5 cm below the LCM or A ≥100% increase in palpable distance, below LCM, for baseline splenomegaly of 5-10 cm or A 50% increase in palpable distance, below LCM, for baseline splenomegaly of >10 cm or Leukemic transformation confirmed by a bone marrow blast count of ≥20% or A peripheral blood blast content of ≥20% associated with an absolute blast count of ≥1 X 10(9)/L that lasts for at least 2 weeks
Stable disease	Belonging to none of the above listed response categories
Relapse	No longer meeting criteria for at least CI after achieving CR, PR, or CI, or Loss of anemia response persisting for at least 1 month or Loss of spleen response persisting for at least 1 month
Recommendations for assessing treatment-induced cytogenetic and molecular changes	

Response category	Definition
Cytogenetic remission	
At least 10 metaphases must be analyzed for cytogenetic response evaluation and requires confirmation by repeat testing within 6 months window
 
CR: eradication of a preexisting abnormality
 
PR: <math>\geq 50\%</math> reduction in abnormal metaphases
 
(partial response applies only to patients with at least ten abnormal metaphases at baseline)

Molecular remission	
Molecular response evaluation must be analyzed in peripheral blood granulocytes and requires confirmation by repeat testing within 6 months window
 
CR: Eradication of a pre-existing abnormality
 
PR: <math>\geq 50\%</math> decrease in allele burden
 
(partial response applies only to patients with at least 20% mutant allele burden at baseline)

Cytogenetic/molecular relapse	
Re-emergence of a pre-existing cytogenetic or molecular abnormality that is confirmed by repeat testing

Tefferi et al. (2013) Revised response criteria for myelofibrosis: International Working (IWG-MRT) and European LeukemiaNet (ELN) consensus report Group-Myeloproliferative Neoplasms Research and Treatment. Blood; 2013 122: 1395-1398

EMH, extramedullary hematopoiesis (no evidence of EMH implies the absence of pathology- or imaging study-proven nonhepatosplenic EMH); LCM, left costal margin; UNL, upper normal limit.

†Grading of MF is according to the European classification

Thiele et al. European consensus on grading bone marrow fibrosis and assessment of cellularity. Haematologica. 2005;90:1128.

It is underscored that the consensus definition of a CR bone marrow is to be used only in those patients in which all other criteria are met, including resolution of leukoerythroblastosis. It should also be noted that it was a particularly difficult task for the working group to reach a consensus regarding what represents a complete histologic remission.

‡Immature myeloid cells constitute blasts + promyelocytes + myelocytes + metamyelocytes + nucleated red blood cells. In splenectomized patients,  $<5\%$  immature myeloid cells is allowed.

§See above for definitions of anemia response, spleen response, and progressive disease. Increase in severity of anemia constitutes the occurrence of new transfusion dependency or a  $\geq 20\%$  decrease in hemoglobin level from pretreatment baseline that lasts for at least 12 weeks. Increase in severity of thrombocytopenia or neutropenia is defined as a 2-grade decline, from pretreatment baseline, in platelet count or absolute neutrophil count, according to the Common Terminology Criteria for Adverse Events (CTCAE) version 4.0. In addition, assignment to CI requires a minimum platelet count of  $\geq 25\,000 \times 10^9/L$  and absolute neutrophil count of  $\geq 0.5 \times 10^9/L$ .

||Applicable only to patients with baseline hemoglobin of  $<100\text{ g/L}$ . In patients not meeting the strict criteria for transfusion dependency at the time of study enrollment (see as follows), but have received transfusions within the previous month, the pre-transfusion hemoglobin level should be used as the baseline.

^Transfusion dependency before study enrollment is defined as transfusions of at least 6 units of packed red blood cells (PRBC), in the 12 weeks prior to study enrollment, for a hemoglobin level of  $<85\text{ g/L}$ , in the absence of bleeding or treatment-induced anemia. In addition, the most recent transfusion episode must have occurred in the 28 days prior to study enrollment. Response in transfusion-dependent patients requires absence of any PRBC transfusions during any consecutive “rolling” 12-week interval during the treatment phase, capped by a hemoglobin level of  $\geq 85\text{ g/L}$ .

Response category	Definition
	#In splenectomized patients, palpable hepatomegaly is substituted with the same measurement strategy. **Spleen or liver responses must be confirmed by imaging studies where a $\geq 35\%$ reduction in spleen volume, as assessed by MRI or CT, is required. Furthermore, a $\geq 35\%$ volume reduction in the spleen or liver, by MRI or CT, constitutes a response regardless of what is reported with physical examination.
	††Symptoms are evaluated by the MPN-SAF TSS.  The MPN-SAF TSS is assessed by the patients themselves and this includes fatigue, concentration, early satiety, inactivity, night sweats, itching, bone pain, abdominal discomfort, weight loss, and fevers. Scoring is from 0 (absent/as good as it can be) to 10 (worst imaginable/as bad as it can be) for each item. The MPN-SAF TSS is the summation of all the individual scores (0-100 scale). Symptoms response requires $\geq 50\%$ reduction in the MPN-SAF TSS. ††Progressive disease assignment for splenomegaly requires confirmation by MRI or computed tomography showing a $\geq 25\%$ increase in spleen volume from baseline. Baseline values for both physical examination and imaging studies refer to pretreatment baseline and not to post-treatment measurements.
	Symptoms are evaluated by the MPN-SAF TSS.  The MPN-SAF TSS is assessed by the patients themselves and this includes fatigue, concentration, early satiety, inactivity, night sweats, itching, bone pain, abdominal discomfort, weight loss, and fevers. Scoring is from 0 (absent/as good as it can be) to 10 (worst imaginable/as bad as it can be) for each item. The MPN-SAF TSS is the summation of all the individual scores (0-100 scale). Symptoms response requires $\geq 50\%$ reduction in the MPN-SAF TSS. Progressive disease assignment for splenomegaly requires confirmation by MRI or computed tomography showing a $\geq 25\%$ increase in spleen volume from baseline. Baseline values for both physical examination and imaging studies refer to pretreatment baseline and not to post-treatment measurements.

**Appendix N: Criteria for Response assessment in polycythemia vera  
(based on modified IWG-MRT guidelines and European LeukemiaNet  
(ELN) consensus report)**

Response categories	Required criteria
Complete remission	
Durable resolution of disease-related signs including palpable hepatosplenomegaly, large symptoms improvement† AND
 
Durable peripheral blood count remission, defined as Ht lower than 45% without phlebotomies; platelet count <math>\leq 400 \times 10^9/L</math>, WBC count <math>< 10 \times 10^9/L</math>, AND
 
Without progressive disease, and absence of any hemorrhagic or thrombotic event, AND
 
Bone marrow histological remission defined as the presence of age-adjusted normocellularity and disappearance of tri-linear hyperplasia, and absence of >grade 1 reticulin fibrosis

Partial remission	
Durable resolution of disease-related signs including palpable hepatosplenomegaly, large symptoms improvement† AND
 
Durable peripheral blood count remission, defined as Ht lower than 45% without phlebotomies; platelet count <math>\leq 400 \times 10^9/L</math>, WBC count <math>< 10 \times 10^9/L</math>, AND
 
Without progressive disease, and absence of any hemorrhagic or thrombotic event, AND
 
Without bone marrow histological remission defined as persistence of tri-linear hyperplasia.

No response	Any response that does not satisfy partial remission
Progressive disease	Transformation into post-PV myelofibrosis, myelodysplastic syndrome or acute leukemia ‡

Molecular response is not required for assignment as complete response or partial response. Molecular response evaluation requires analysis in peripheral blood granulocytes. Complete response is defined as eradication of a preexisting abnormality. Partial response applies only to patients with at least 20% mutant allele burden at baseline. Partial response is defined as <math>\geq 50\%</math> decrease in allele burden.
 
WBC, white blood cell.
	

†Large symptom improvement (<math>\geq 10</math>-point decrease) in MPN-SAF TSS.
	

‡For the diagnosis of post-PV myelofibrosis, see the IWG-MRT criteria; for the diagnosis of myelodysplastic syndrome and acute leukemia, see WHO criteria.
	

 
1. Barosi G, et al; Revised response criteria for polycythemia vera and essential thrombocythemia: an ELN and IWG-MRT consensus project. Blood 2013;121: 4778-4781
 
 
 
	

**Appendix O: Criteria for Response assessment in Essential thrombocythemia (based on modified IWG-MRT guidelines and European LeukemiaNet (ELN) consensus report)**

Response category	Definition
Complete remission	
Durable resolution of disease-related signs including palpable hepatosplenomegaly, large symptoms improvement,† AND
 
Durable peripheral blood count remission, defined as: platelet count <math>\leq 400 \times 10^9/L</math>, WBC count <math>< 10 \times 10^9/L</math>, absence of leukoerythroblastosis, AND
 
Without signs of progressive disease, and absence of any hemorrhagic or thrombotic events, AND
 
Bone marrow histological remission defined as disappearance of megakaryocyte hyperplasia and absence of >grade 1 reticulin fibrosis.

Partial remission	
Durable resolution of disease-related signs including palpable hepatosplenomegaly, and large symptoms improvement, AND
 
Durable peripheral blood count remission, defined as: platelet count <math>\leq 400 \times 10^9/L</math>, WBC count <math>< 10 \times 10^9/L</math>, absence of leukoerythroblastosis, AND
 
Without signs of progressive disease, and absence of any hemorrhagic or thrombotic events, AND
 
Without bone marrow histological remission, defined as the persistence of megakaryocyte hyperplasia.

No response	Any response that does not satisfy partial remission
Progressive disease	Transformation into PV, post-ET myelofibrosis, myelodysplastic syndrome or acute leukemia ‡

Molecular response is not required for assignment as complete response or partial response. Molecular response evaluation requires analysis in peripheral blood granulocytes. Complete response is defined as eradication of a preexisting abnormality. Partial response applies only to patients with at least 20% mutant allele burden at baseline. Partial response is defined as <math>\geq 50\%</math> decrease in allele burden.
 
WBC, white blood cell.
 
†Large symptom improvement (<math>\geq 10</math>-point decrease) in MPN-SAF TSS.
 
‡For the diagnosis of PV see World Health Organization criteria (WHO); for the diagnosis of post-ET myelofibrosis, see the IWG-MRT criteria; for the diagnosis of myelodysplastic syndrome and acute leukemia, see WHO criteria.
	
